5.4.7 Electrocardiogram (ECG)

A 12-lead ECG will be performed at **Screening**. At select study centers, up to 25 patients may be specifically consented for intensive PK sampling and concurrent ECGs as defined below:

Schedule: Intensive PK blood sampling will be at pre-dose and 2, 4, 8, 12, and 24 hours post-dose on **Cycle 1, Day 1** and on **Cycle 1, Day 8 (±3 days)**. The 12-hour and 24-hour PK samples must be collected prior to the second daily dose. A local 12-lead ECG will be obtained just before each PK blood sample on both Day 1 and Day 8. If the patient has interrupted continuous poziotinib dosing, clear dosing documentation must be done in order to assess suitability of further PK sampling and ECG recording.

In addition, if a patient presents with a potentially drug-related Grade ≥ 3 AE, a PK sample should be collected as soon as possible, if feasible, following the onset of the AE in order to characterize the PK. Documentation of last dose timing prior to the event is required.

5.4.8 Cardiac Ejection Fraction

For patients who are at high risk of cardiac disease, as determined by the Investigator, cardiac ejection fraction may be assessed by either echocardiogram or multi-gated acquisition (MUGA) scan at Screening, and the investigator can order subsequent tests based on institutional standard of care.

5.4.9 Tumor Assessment

Tumor assessment for study patient's eligibility must be performed by Investigators using computed tomography (CT), positron emission tomography (PET)/CT, or magnetic resonance imaging (MRI) for non-brain organs and MRI for brain at **Screening** up to 30 days prior to **Cycle 1, Day 1**. Imaging studies performed prior to the signing of Informed Consent as part of the site's routine standard of practice are allowed at the discretion of the Sponsor as the Screening assessment. Brain MRI must be performed to assess the brain metastasis status at the screening per eligibility criteria. This information is to be discussed with the Sponsor's Medical Monitor before the patient is enrolled in the study. **Baseline** tumor assessment will be performed within 2 weeks prior to, or on **Cycle 1, Day 1**. Post-Baseline tumor assessments must be performed at **Cycle 2 Day 1**, at **Cycle 3 Day 1**, and every 8 weeks thereafter until patient discontinuation.

Each subsequent tumor assessment must use the same radiologic technique as in Baseline, either CT, PET/CT, or MRI. Tumor assessments will be made according to RECIST, version 1.1 [14] using appropriate radiologic imaging or other techniques. For radiographic assessment, CT, PET/CT, or MRI must be performed at every assessment.

In Cohort 4, tumor assessments will be made using appropriate radiologic imaging techniques as per RECIST 1.1 and/or the RANO criteria [15].

Measurable and non-measurable lesions should be documented appropriately.

Tumor assessment is based on the study investigator's assessment with local radiology review and report according to the RECIST 1.1 and/or RANO (for **Cohort 4**) criteria for response evaluation.

5.4.10 Tissue, Plasma, and Whole Blood Samples Retained

5.4.10.1 Tissue Samples

Tissue samples at **Screening**, if available, are acquired prior to **Cycle 1, Day 1** during the screening period. If possible, tumor tissue samples from a biopsy when progression occurs during the study should be collected. This is not mandatory but is encouraged. The tumor tissue will be used for genetic analysis (DNA and or RNA sequencing) to understand poziotinib response and resistance mechanisms.

5.4.10.2 Plasma Samples

Plasma samples are required at baseline (prior to start of study treatment), and optional on the day of each on-study imaging session, beginning at the 8-week imaging session, once every 8 weeks with imaging scan. The plasma samples will be used for genetic analysis (DNA sequencing) to understand poziotinib response mechanism and progression of disease. Guardant's 360 or FoundationACT assays will be used, Plasma sample collection and storage will follow vendors' standard procedures as described in the vendors' Laboratory Manual.

5.4.10.3 Whole Blood Samples

Whole blood samples will be collected once at **Screening** or during the study for pharmacogenomic analysis.

5.4.11 Concomitant Medications

All medications administered from Screening to the Safety Follow-up Visit will be recorded on the CRF. A concomitant medication is any medication a patient is using from Cycle 1, Day 1 to the Safety Follow-up Visit. Poziotinib is not considered a concomitant medication.

All concomitant medications recorded at study entry must have a related, ongoing concomitant illness listed under the medical history at the time of patient entry into the trial. Patients may continue to use any ongoing medications not prohibited by the protocol.

All prescription and over-the-counter medications at trial entry as well as any new medications started during the trial must be documented on the CRF and in the source documents. The documentation should continue until 30 (± 5) days after the last dose of poziotinib.

Premedications (such as antiemetics) used for supportive care are allowed as per institutional standards or guidelines and Investigator discretion.

Other supportive and palliative therapies may be allowed during the study upon prior authorization from Sponsor's Medical Monitor.

5.4.11.1 Possible Drug Interactions

Poziotinib is a substrate for cytochrome P450 (CYP) 3A4 and 2D6 enzymes. Patients may be taking medications that are strong inhibitors or inducers of these two enzymes (**Table 1**). The plasma concentration of poziotinib could be different in these patients. The Investigator should try to substitute a medication that is not a strong inhibitor/inducer of these enzymes, if possible. If there is not an available substitute for a medication that a patient is taking or the patient is not

willing to change medications, the Investigator must monitor the patient closely for possible AEs or changes in response.

Poziotinib is also a moderate inhibitor of CYP2C8 and CYP2D6, so patients who take medications that are sensitive substrates for these two enzymes (**Table 1**) should be followed closely for possible changes in the patient's response to these medications. Patients should be advised that grapefruit juice and St. John's Wort should be avoided during the study treatment.

Table 1 Examples of Important Clinical Inhibitors/Inducers/Substrates for P450 Enzymes Involved in the Metabolism of Poziotinib

CYP	Strong Inhibitor	Strong Inducer	Sensitive Substrate
2D6	Bupropion, Fluoxetine, Paroxetine, Quinidine, Terbinafine	None	Atomoxetine, Desipramine, Dextromethorphan, Eliglustat, Nebivolol, Nortriptyline, Perphenazine, Tolterodine, Venlafaxine
3A4	Boceprevir, Cobicistat, Conivaptan, Danoprevir and Ritonavir, Elvitegravir and Ritonavir, Grapefruit Juice, Indinavir and Ritonavir, Itraconazole, Ketoconazole, Lopinavir and Ritonavir, Paritaprevir and Ritonavir and (Ombitasvir and/or Dasabuvir), Posaconazole, Ritonavir, Saquinavir and Ritonavir, Telaprevir, Tipranavir and Ritonavir, Troleandomycin, Voriconazole	Carbamazepine, Enzalutamide, Mitotane, Phenytoin, Rifampin, St. John's Wort	Not Applicable
2C8	Not Applicable	Not Applicable	Repaglinide

Source: <https://www.fda.gov/drugs/developmentapprovalprocess/developmentresources/druginteractionslabeling/ucm093664.htm>

5.4.11.2 Premedication and Supportive Treatment

Pre-medications, as per Institutional standard of care as determined by the Investigator, should be administered before poziotinib on **Day 1**. All supportive medications for potential diarrhea and rash management should be distributed to the patient on **Day 1** with instructions on their use.

Supportive medications, including early steroid use, should be considered even in the presence of low-grade "on-target" toxicity (eg, rash, diarrhea).

5.4.11.2.1 Diarrhea Management

Spectrum will supply loperamide for diarrhea management. Diarrhea should be monitored very closely. Diarrhea can be managed per standard of care as determined by the Investigator, Institutional Guidelines, or considering the algorithm in **Appendix 3**.

5.4.11.2.2 Mucositis Management

Mucositis/stomatitis can be treated in a supportive manner aiming to control symptoms. Prophylactic methods to reduce or prevent mucositis/stomatitis include:

- Avoidance of spicy, acidic, or irritating foods and alcoholic drinks
- Use of solutions such as saline (diluted solution with saltwater and baking soda by dissolving a ½ teaspoon of salt and 1 teaspoon of baking soda in approximately 1 liter of water) and using this solution every 4 hours
- Use of Nystatin solution
- Use of Magic Mouthwash (for instance, a combination of viscous lidocaine 2% + Mylanta + diphenhydramine elixir + prednisolone solution)

5.4.11.2.3 Rash Management

Rash may be managed according to the algorithm in [Appendix 4](#) and/or per standard of care as determined by the Investigator or Institutional Guidelines.

. Supportive intervention, including early steroid use, should be considered even in the presence of low-grade “on-target” toxicity (eg, rash, diarrhea).

5.4.11.2.4 Paronychia management

Paronychia may be managed according to the algorithm in [Appendix 5](#) and/or per standard of care as determined by the Investigator or Institutional Guidelines

5.4.11.3 Uses of Warfarin or Other Coumadin-Derived Anticoagulants

Warfarin or other coumadin-derived anticoagulants should be used cautiously during treatment with poziotinib. When it cannot be avoided, regular monitoring of INR is required, and prior authorization from the Sponsor’s Medical Monitor is required.

No additional cytotoxic agents, biologic therapy, or immune response modifiers for cure-intent purpose are to be administered to patients until study treatment has been discontinued.

5.4.11.4 Prohibited Therapies or Medications

No other anti-cancer therapy, including chemotherapy, radiation therapy, immunotherapy, target therapy (including HER2 targeted therapy), biologics, or experimental medications, are permitted during the trial with the exception of focal radiation therapy for bone pain palliation. Any disease progression that requires anti-tumor therapy will be a cause for discontinuation from the study.

6 STUDY DRUG AND PHARMACEUTICAL INFORMATION

Study treatment is to be handled and administered according to the study sites’ regulations for the handling and administration of cytotoxic anticancer agents.

6.1 Poziotinib

Poziotinib will be supplied by Spectrum.

6.1.1 Poziotinib Composition and Formulations

The poziotinib drug substance is a hydrochloride salt of poziotinib and is formulated as a tablet for oral administration. Poziotinib tablets are supplied in 2.0-mg and 8.0-mg dose strengths and contain 2.0 mg and 8.0 mg of poziotinib hydrochloride salt, respectively.

6.1.2 Poziotinib Administration

Poziotinib is supplied as 8-mg and 2-mg tablets and will be administered on an outpatient basis orally twice daily.

Dosing Regimen

The starting dose of poziotinib is 8 mg twice per a day (BID). Poziotinib will be self-administered by the patient orally, with food and a glass of water, at approximately the same time(s) each day during each 28-day cycle.

The first dose should be taken in the morning and the second dose should be taken approximately 8 to 12 hours later. If a dose is missed, it should be taken once remembered or with the next dose if on the same day.

6.1.3 Poziotinib Storage and Handling

Poziotinib supplies must be stored in a secure, limited-access location under the storage conditions specified on the drug supply label.

KEEP THIS AND ALL MEDICATIONS OUT OF THE REACH OF CHILDREN.

6.1.4 Poziotinib Dose Modification Recommendations

If needed, the initial dose (8 mg BID) may be reduced by 2 mg for each dose (ie 12 mg per day divided into 6 mg BID doses) at the Investigator's discretion and the Sponsor should be notified. If further dose reduction is required, the next dose should be reduced by a total of 2 mg/day (ie 10 mg per day divided into a 6 mg and 4 mg dose per day) and the Sponsor should be notified. Any further reductions in dose must be discussed a priori with the Sponsor's Medical Monitor and approval is required.

No dose reductions below 8 mg total dose/day are allowed.

Table 2 Poziotinib Dose Modifications Recommendations

Related Adverse Event	Grade	Occurrence	
		1	Each Additional Occurrence
Diarrhea	Grade ≥ 3 (Despite adequate anti-diarrhea management)	Stop poziotinib treatment until AE Grade ≤ 1 and then continue treatment at the same dose ^a or Reduce Poziotinib Dose by 2 mg/dose	Reduce Poziotinib Dose by ~1 mg/dose
	Grade ≥ 2 for ≥ 48 hours (Despite adequate diarrhea management)		
Fatigue	Grade ≥ 3		
Mucositis/ Stomatitis	Grade ≥ 3 (Despite adequate management)		
Nausea and/or Vomiting	Grade ≥ 3 (Despite adequate anti-emetics)		
	Grade ≥ 2 for ≥ 48 hours (Despite adequate anti-emetics)		
Rash	Any Grade	Refer to Appendix 4 .	

Related Adverse Event	Grade	Occurrence	
		1	Each Additional Occurrence
LVEF Dysfunction	Grade ≥ 3	Discontinue Treatment	

- a) Supportive medications, including early steroid use, should be considered even in the presence of low-grade “on-target” toxicity (eg, rash, diarrhea)(Appendix 4).

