7 SAFETY ASSESSMENT

7.1 Safety Measures

It is the responsibility of the Principal Investigator to oversee the safety of the patients at their site and to report all AEs/SAEs that are observed or reported during the study, regardless of relationship to investigational drug or clinical significance. The decision to modify the dose of study treatment will be determined by the Investigator based on the decision rules shown in Section 6.1.4.

Safety data will also be reviewed on a regular basis by the Sponsor’s study monitoring team, which includes a Clinical Research Associate (CRA), Medical Monitor, and other personnel from the Spectrum Pharmaceuticals, Inc. or its designee.

Adverse events will be characterized by intensity (severity), causality, and seriousness by the Investigator based on the regulatory definitions included below.

This study will utilize the National Cancer Institute (NCI) Common Terminology Criteria for Adverse Events (CTCAE) Scale Version 5.0 for AE grading.

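### Table 2 sizes dose reductions by occurrence number while the text above it goes by current dose, so the two can differ by 2 mg/day

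*Combined protocol and SAP*

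**What the plan says.** The text of Section 6.1.4 ties each step to the dose the patient is on. From the start, "the initial dose (8 mg BID) may be reduced by 2 mg for each dose (ie 12 mg per day", given as 6 mg BID. If more is needed, "the next dose should be reduced by a total of 2 mg/day", to 10 mg/day given as 6 mg and 4 mg. The Sponsor is notified of each of these two steps. After that, "Any further reductions in dose must be discussed a priori with the" Medical Monitor, whose approval is required, and "No dose reductions below 8 mg total dose/day are allowed".

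Table 2 in the same section is arranged by event and occurrence. At the first occurrence it offers two options: hold until the event settles "and then continue treatment at the same dose", or reduce by 2 mg per dose. For every later occurrence it has one instruction: "Reduce Poziotinib Dose by ~1 mg/dose". The Synopsis carries the same table and text.

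Two other places bear on this. Section 6.1.2 states that "Poziotinib is supplied as 8-mg and 2-mg tablets". Section 7.1 says that the decision to modify the dose "will be determined by the Investigator based on the decision rules shown in Section 6.1.4", which covers both the text and the table.

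**The concern.** The text indexes the reduction by current dose level and the table indexes it by occurrence number. These give the same answer only while each occurrence moves the patient down exactly one level. The table itself allows that link to break, because a first occurrence can pass with no reduction. It may also break if a second type of event starts its own count. An investigator working from the table and one working from the paragraph above it could then prescribe different doses for the same toxicity.

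What is at stake is consistent dosing and clear approval rules. Relative dose intensity is a summarized variable (Section 8.6), and patients who move to the extension study continue at their last dose level (Section 3.1), so an unlisted level could carry forward.

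**Working it through.** **Inputs.** Starting dose 8 mg BID = 16 mg/day (6.1.2). Text: first reduction 2 mg per dose, second reduction 2 mg/day in total (6.1.4). Table 2: 2 mg per dose or no change at occurrence 1, then about 1 mg per dose. Tablets of 8 mg and 2 mg (6.1.2).

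**The text's own figures.** 2 × (8 − 2) = 12 mg/day; 12 − 2 = 10 mg/day. Both reproduce.

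**Same event, dose reduced at occurrence 1.** Table: 16 − 2 × 2 = 12, then 12 − 2 × 1 = about 10. This agrees with the text.

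**Case 1: same event, hold and resume at occurrence 1.** The dose stays at 16 mg/day. At recurrence:
- Table, read literally: 2 × (8 − 1) = about 14 mg/day, or 14/16 = 87.5% of the starting dose.
- Text, first reduction from 8 mg BID: 2 × (8 − 2) = 12 mg/day, or 12/16 = 75%.
- Gap: 14 − 12 = 2 mg/day, 2/16 = 12.5% of the starting dose. The table is the milder of the two.

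The supplied tablets give only even doses, so 7 mg BID is not possible, but 8 + 6 = 14 mg/day is.

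**Case 2: patient already at 12 mg/day, first occurrence of a different event.** The answer depends on how occurrences are counted, which Table 2 does not say.
- Counted per event, table's reduction option: 12 − 2 × 2 = 8 mg/day, or 8/16 = 50%. The table mentions no approval.
- Text, next step from 12: 12 − 2 = 10 mg/day, or 10/16 = 62.5%. Going lower needs prior approval.
- Gap: 10 − 8 = 2 mg/day, again 12.5% of the starting dose. Here the table is the harsher.
- Counted across events, this is an additional occurrence: 12 − 2 × 1 = about 10 mg/day, which agrees with the text.

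| Situation | Table 2 | Text | Gap |
|---|---|---|---|
| Reduced at first occurrence, same event recurs | about 10 | 10 | 0 |
| Held and resumed at 16, same event recurs | about 14 | 12 | 2 |
| At 12, first occurrence of another event, counted per event | 8 | 10 | 2 |
| At 12, another event, counted across events | about 10 | 10 | 0 |

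(All in mg/day.)

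**Reach.** If, as the layout suggests, the two cells span the diarrhea (2), fatigue (1), mucositis/stomatitis (1) and nausea/vomiting (2) rows, they cover 6 of the 8 rows. Rash is sent to Appendix 4, and LVEF dysfunction leads to discontinuation. The spanning is an inference from a table whose layout was lost in extraction.

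**The case against.** The best reply is that the text already settles the matter. It stands directly above both copies of the table. A patient who was held and resumed is still on the initial dose, so the text gives 12 mg/day. Section 7.1 points to the whole of Section 6.1.4, so the table cell is not the rule by itself. The approximate 1 mg per dose was probably shorthand for the step from 12 to 10, since 6 + 4 is on average 1 mg per dose below 6 + 6. Section and table are headed as recommendations, the first reduction is at the investigator's discretion, and the Sponsor hears of it.

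Most of this stands, and it limits the consequence. It does not remove the mismatch: the cell is not restricted to the 12-to-10 step, so the reader has to infer the intent, and discretion over whether to reduce does not say which dose follows.

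Some stronger readings are tempting but not supported. A reader might infer that 14 mg/day is forbidden or cannot be dispensed. No section forbids it, it can be given as 8 + 6 mg, and every dose in the two cases lies within 8 to 16 mg/day, so the floor is not breached. A reader might also infer that sites will in fact diverge, or that the response-rate analysis is affected. The documents give no frequency for either case, and none of the design figures depends on this table.

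**Conclusion.** The point holds as a minor inconsistency. Table 2 and the text of Section 6.1.4 give different doses in at least one case: recurrence after hold-and-resume, about 14 against 12 mg/day. This rests on a literal reading of the recurrence cell. They differ in a second case, 8 against 10 mg/day with no approval stated in the table, only on the assumption that occurrences are counted per event. The size is 2 mg/day in each, 12.5% of the starting dose, in opposite directions. Where the dose is reduced at the first occurrence and the same event recurs, table and text agree. The frequency is unknown, and no efficacy figure or error rate changes.

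**What to change.** Make the same change in both copies of the table (Synopsis and Section 6.1.4):

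- **Occurrence 1 cell:** keep the hold-and-resume option and replace the 2 mg/dose reduction with: reduce to the next lower dose level.
- **Each Additional Occurrence cell:** replace the ~1 mg/dose instruction with: reduce to the next lower dose level.
- **Note under the table:** Dose levels: 16 (8+8), 12 (6+6), 10 (6+4) mg/day; the step depends on the current dose, not the occurrence number; any reduction below 10 mg/day (not below 8 mg/day), or any other dose level, only with prior Medical Monitor approval.

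This restates the text's own ladder, floor and approval rule, and Appendix 4 already speaks of a next lower dose for Grade 3 rash. The one addition is that an unlisted level such as 14 mg/day would need prior approval; it stays available where there is a reason for it. With the step tied to the current dose, the per-event or across-event counting question no longer affects the size of a reduction.

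The cost is two cells and one note, in two places. Holds, discontinuation rules, visits and patient numbers do not change.

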6.2 Comparator Treatment

No comparator is used in this study.

7 SAFETY ASSESSMENT

7.1 Safety Measures

It is the responsibility of the Principal Investigator to oversee the safety of the patients at their site and to report all AEs/SAEs that are observed or reported during the study, regardless of relationship to investigational drug or clinical significance. The decision to modify the dose of study treatment will be determined by the Investigator based on the decision rules shown in Section 6.1.4.

Safety data will also be reviewed on a regular basis by the Sponsor’s study monitoring team, which includes a Clinical Research Associate (CRA), Medical Monitor, and other personnel from the Spectrum Pharmaceuticals, Inc. or its designee.

Adverse events will be characterized by intensity (severity), causality, and seriousness by the Investigator based on the regulatory definitions included below.

This study will utilize the National Cancer Institute (NCI) Common Terminology Criteria for Adverse Events (CTCAE) Scale Version 5.0 for AE grading.

7.2 Adverse Events

An AE is defined as any untoward medical occurrence in a patient or clinical investigation patient, temporally associated with the use of a medicinal product, whether or not considered related to the medicinal product. Therefore, an AE can be any unfavorable and unintended sign (including an abnormal laboratory finding), symptom, or disease (new or exacerbated) temporally associated with the use of a medicinal product. A treatment-emergent AE (TEAE) is any AE that occurs from the first dose of study treatment until 30 (± 5) days after the last dose of study treatment.

The study will record all AEs according to the information in Section 7.3.

Examples of AEs **include**:

- Exacerbation of a chronic or intermittent pre-existing condition including either an increase in frequency and/or intensity of the condition
- New conditions detected or diagnosed after investigational product administration.
- Signs, symptoms, or the clinical sequelae of a suspected drug interaction

- Signs, symptoms, or the clinical sequelae of a suspected overdose of either investigational drug or a concurrent medication
- AEs may include pre-treatment or post-treatment events that occur as a result of protocol-mandated procedures (e.g., invasive procedures)

Abnormal laboratory results are to be recorded as AEs, if any of the following conditions are met:

- The abnormal laboratory value leads to a therapeutic intervention
- The abnormal laboratory value is considered to be clinically significant by the Investigator
- The abnormal laboratory value is predefined as an AE in the protocol or in another document communicated to the Investigator by Spectrum or designee

Examples of events that **do not** constitute AEs include:

- Medical or surgical procedures (e.g., endoscopy, appendectomy); the condition that leads to the procedure is an AE
- Situations where an untoward medical occurrence does not occur (e.g., social and/or convenience admission to a hospital)
- Anticipated day-to-day fluctuations of pre-existing disease(s) or condition(s) present or detected at the start of the study that does not worsen
- Planned and prescheduled hospitalizations and procedures
- Progressive disease

The adverse events of special interest identified with poziotinib treatment include diarrhea, skin rash, stomatitis, paronychia, and pneumonitis.

